≥ 13 to <18 years of age (female only)	9.5 to 10.4 5.88 to 6.48	8.5 to < 9.5 5.25 to < 5.88	6.5 to < 8.5 4.03 to < 5.25	< 6.5 < 4.03
57 days of age to < 13 years of age (male and female)	9.5 to 10.4 5.88 to 6.48	8.5 to < 9.5 5.25 to < 5.88	6.5 to < 8.5 4.03 to < 5.25	< 6.5 < 4.03
36 to 56 days of age (male and female)	8.5 to 9.6 5.26 to 5.99	7.0 to < 8.5 4.32 to < 5.26	6.0 to < 7.0 3.72 to < 4.32	< 6.0 < 3.72
22 to 35 days of age (male and female)	9.5 to 11.0 5.88 to 6.86	8.0 to < 9.5 4.94 to < 5.88	6.7 to < 8.0 4.15 to < 4.94	< 6.7 < 4.15
8 to ≤ 21 days of age (male and female)	11.0 to 13.0 6.81 to 8.10	9.0 to < 11.0 5.57 to < 6.81	8.0 to < 9.0 4.96 to < 5.57	< 8.0 < 4.96
≤ 7 days of age (male and female)	13.0 to 14.0 8.05 to 8.72	10.0 to < 13.0 6.19 to < 8.05	9.0 to < 10.0 5.59 to < 6.19	< 9.0 < 5.59

¹ The conversion factor used to convert g/dL to mmol/L is 0.6206 and is the most commonly used conversion factor. For grading hemoglobin results obtained by an analytic method with a conversion factor other than 0.6206, the result must be converted to g/dL using the appropriate conversion factor for the particular laboratory; LLN = lower limit of normal according to local or central laboratory

Low levels of haemoglobin reaching grades 3 and 4 may result in transient or permanent treatment discontinuation (see reference values in the Laboratory Specifications).

Table 6: Grading of adverse events due to low levels of white blood cells

Parameter	Grade 1 Mild	Grade 2 Moderate	Grade 3 Severe	Grade 4 Potentially Life-Threatening
WBC, Decreased (cells/mm³; cells/L)				
> 7 days of age	2,000 to 2,499 2.000×10^9 to 2.499×10^9	1,500 to 1,999 1.500×10^9 to 1.999×10^9	1,000 to 1,499 1.000×10^9 to 1.499×10^9	< 1,000 $< 1.000 \times 10^9$
≤ 7 days of age	5,500 to 6,999 5.500×10^9 to 6.999×10^9	4,000 to 5,499 4.000×10^9 to 5.499×10^9	2,500 to 3,999 2.500×10^9 to 3.999×10^9	< 2,500 $< 2.500 \times 10^9$

Decrease in white blood cell counts of grades 3 and 4 may result in transient or permanent treatment discontinuation. (see reference values in the Laboratory Specifications).

Table 7: Grading of adverse events due to low levels of neutrophils

Parameter	Grade 1 Mild	Grade 2 Moderate	Grade 3 Severe	Grade 4 Potentially Life-Threatening
Absolute Neutrophil Count (ANC), Low (cells/mm³; cells/L)				
> 7 days of age	800 to 1,000 0.800×10^9 to 1.000×10^9	600 to 799 0.600×10^9 to 0.799×10^9	400 to 599 0.400×10^9 to 0.599×10^9	< 400 $< 0.400 \times 10^9$

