6.4.1.2 Secondary Efficacy Endpoints

The key secondary efficacy endpoint is

- Response to therapy (including complete response and partial response) in the SAOL phase from Week 10 onwards and observed at least at 2 consecutive visits at least 2 weeks apart during the SAOL phase

Other secondary efficacy endpoints include the following:

- Best response to therapy during the SAOL phase (including complete response and partial response and disease improvement)

- Duration of response to therapy (including complete response and partial response) during the SAOL phase
- Disease reactivation rate (ie, number of disease reactivations experienced per week while each subject is on the study treatment during the SAOL phase)
- Treatment failures (ie, patients who experience at least one disease reactivation), during the RW phase
- Intensity of disease reactivations (defined by the level of activity given by the mAIDAI – both objective and subjective criteria), during the RW phase and the SAOL phase
- Serum CRP during the RW phase and the SAOL phase
- Serum ferritin during the RW phase and the SAOL phase
- Improvement of fevers (if present at baseline) during the RW phase and the SAOL phase
- Improvement of hepato/splenomegaly (if present at baseline) during the RW phase and the SAOL phase
- Improvement in serum albumin and liver transaminases, anemia and/or platelet count (if present at baseline) during the RW phase and the SAOL phase
- Number of hospitalizations and hospital length of stay during the RW phase and the SAOL phase
- PGA during the RW phase and the SAOL phase
- Patient's or caregiver's qualitative evaluation of health status
- Presence of skin rash (evolution if present at baseline or appearance during the study) during the RW phase and the SAOL phase
- Tolerance to oral/enteral nutrition for hospitalized patients with intestinal dysfunction that was present at baseline during the RW phase and the SAOL phase
- Improvement of stool output for hospitalized patients if intestinal dysfunction was present at baseline during the RW phase and the SAOL phase

Active disease upon enrolment is defined as:

- Increased inflammatory markers, i.e., serum ferritin levels ≥ 500 ng/mL or serum CRP $\geq 2 \times$ ULN, and
- Active clinical disease as evidenced by mAIDAI ≥ 4 or CNS manifestations (i.e., seizures, altered mental status, signs of increased intracranial pressure, chronic papilledema, loss of vision, other sensorineural deficiencies, etc.)

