- As the date of onset of the TEAE of interest minus the date of first dose of study drug plus one, divided by 365.25, for those subjects who experience the TEAE of interest; or
- As the date of last dose of study drug plus 28 days, minus the date of first dose of study drug plus one, divided by 365.25, for those subjects who do not experience the TEAE of interest.

One PEY is the equivalent of one patient exposed to study drug for one year. Two patients who are exposed to study drug for half a year contribute one PEY. The total PEY of a treatment group is the sum of the person exposure years of each patient in that treatment group. Exposure-adjusted TEAE incidence will be summarized per 100 PEY as the number of patients with an event for whom person-time is available, divided by the total PEY for each treatment group and multiplied by 100. Exposure-adjusted TEAE incidence will be summarized separately for the SAOL phase and the RW phase.

Adverse event data will be presented in data listings by patient, treatment group, and event. Serious AEs, AEs leading to discontinuation of the study drug, and AESIs will be presented in separate data listings.

7.5.3 *Deaths, Other Serious Adverse Events, and Other Significant Adverse Events*

All deaths during the study as reported on the End of Treatment (SAOL), End of Treatment (RW), Study Completion/Study Discontinuation, and Adverse Event eCRFs will be listed by patient, to include the primary cause of death. Serious AEs, AEs leading to study drug withdrawal, interruption, or dose reduction of the study drug, and AESIs will be provided in separate patient data listings. AESIs include events that constitute an injection site reaction, including pruritus, erythema, and swelling.

7.5.4 *Clinical Laboratory Evaluation*

All descriptive summaries of laboratory results will be based on data analyzed by the central laboratory and presented in Système International (SI) units, as suggested by the Center for Biologics Evaluation and Research and the Center for Drug Evaluation and Research *Position on Use of SI Units for Lab Tests* (Oct 2013). All data will be included in by-patient data listings. Laboratory measurements identified as abnormal (ie, outside the normal range) will also be listed separately by patient, laboratory test, and unit. In addition, normal ranges provided by the central laboratory will be presented in a separate listing.

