Clinical laboratory measurements including serum chemistry, hematology, coagulation, and erythrocyte sedimentation rate will be summarized separately for the SAOL phase and the RW phase by treatment group. Descriptive statistics will be presented for

observed values and changes from each respective baseline at each visit where parameters were scheduled to be collected per the clinical study protocol.

Where applicable, laboratory results will be classified as “low,” “normal,” or “high” with respect to the parameter-specific reference ranges (ie, below the lower limit of the normal range, within the normal range, or above the upper limit of the normal range). Three-by-three contingency tables will be presented for each study phase and laboratory parameter to summarize the shift from the baseline category to the worst post-baseline measurement, defined as the value numerically farthest outside of the normal range across all post-baseline visits through the end of the study. Summary results will include the count and percentage of patients within each shift category and treatment group. Percentages will be based on the number of patients with a non-missing baseline value and at least one non-missing post-baseline value.

Where applicable, hematology, chemistry, and coagulation results for selected parameters will be assigned a toxicity grade based on the U.S. Department of Health and Human Services *Common Terminology Criteria for Adverse Events (CTCAE)*, version 5.0 (27 Nov 2017). If the quantitative criteria for grading are equivalent for two grades and the differentiation is described by clinical interventions, the clinical intervention component will not be considered and the highest CTCAE grade will be assigned. Similarly, death related to AE (ie, Grade 5) cannot be determined with available laboratory-based data collection and, thus, will not be summarized as a category. Laboratory parameters that include multiple sets of criteria for each direction (eg, separate criteria for potassium measures to assess hyperkalemia and hypokalemia) will be summarized separately to reflect each set of criteria.

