Five-by-five contingency tables will be presented by study phase for lab tests where toxicity grading can be applied, to summarize the shift from the baseline grade to the worst post-baseline grade. Grades will be presented as none (Grade 0; ie, measurement did not meet any CTCAE criteria for Grades 1 through 4), mild (Grade 1), moderate (Grade 2), severe (Grade 3), or life-threatening (Grade 4). Summary results will include the count and percentage of patients within each shift category. Percentages will be based on the number of patients with a non-missing baseline value and at least one non-missing post-baseline value.

7.5.5 *Vital Signs, Physical Findings, and Other Observations Related to Safety*

7.5.5.1 *Vital Signs*

Vital sign parameter measurements will be summarized by study phase and treatment group. Descriptive statistics will be presented for results and change from phase-specific baseline at each visit where parameters were scheduled to be collected. Daily temperatures will be listed. In addition, the number of days where fever is present, defined as temperature above 38 °C, will be presented by month for each subject.

7.5.5.2 *Local Tolerability Index Assessment*

The local tolerability index assesses severity of symptoms for each dosing day. For each symptom, the worst severity reported for any day will be summarized with counts and percentages of patients in each category by study phase and treatment group.

7.5.5.3 *Skin Rash*

The presence and severity of a skin rash will be evaluated at baseline and each post-baseline visit. The number and percent of patients will be presented by study phase, visit, and treatment group for patients with a skin rash present and for each level of severity (mild, moderate, or severe). At post-baseline visits within each phase, the number and percent of patients with the rash at the phase-specific baseline still present and by change category will be presented by treatment group.

7.5.5.4 *Immunogenicity Evaluation*

Blood levels of antibodies to IL-18BP antibodies TA (anti-rh-IL-18BP) will be summarized by treatment group, separately for each study phase. Descriptive statistics will be presented for results and change from phase-specific baseline at each visit where blood samples were scheduled for collection. Blood levels for anti-rh-IL-18BP will also be presented graphically over time for each individual patient.

7.5.5.5 *Physical Examination*

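### The 3x3 laboratory shift tables keep one worst value per patient regardless of direction, so a high count can displace a severe low count of the same parameter

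*SAP*

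**What the plan says.** SAP 7.5.4 classifies laboratory results as low, normal or high against the reference range and tabulates the shift from baseline: "Three-by-three contingency tables will be presented for each study phase and laboratory parameter". The post-baseline side of each table is a single value per patient, the "worst post-baseline measurement, defined as the value numerically farthest outside of the normal range across all post-baseline visits". Nothing in that definition separates low from high.

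The same section plans a second set of shift tables by CTCAE grade: "Five-by-five contingency tables will be presented by study phase for lab tests where toxicity grading can be applied". Grading is limited: "Where applicable, hematology, chemistry, and coagulation results for selected parameters will be assigned a toxicity grade". The selected parameters are not listed. Where a parameter has criteria in both directions, the SAP splits them: "eg, separate criteria for potassium measures to assess hyperkalemia and hypokalemia) will be summarized separately to reflect each set of criteria".

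Two further displays matter here. SAP 7.5.4 states that "Laboratory measurements identified as abnormal (ie, outside the normal range) will also be listed separately by patient, laboratory test, and unit". It also plans by-visit descriptive statistics, which under SAP 7.1.1 include the minimum and maximum.

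**The concern.** A low and a high value of the same parameter are two different safety findings. A table with room for only one of them per patient must drop the other. The choice is made by absolute distance in the parameter's own units, and for counts that scale is lopsided: the low side can be no larger than the lower limit itself, while the high side is open.

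Both directions are plausible in this trial. Patients have inflammatory disease and receive 28-day dexamethasone courses that can be repeated in the SAOL phase. Cytopenia is an item of the mAIDAI. Low white cells and low neutrophils have their own grading tables in Protocol 17.6, and the protocol attaches consequences to them: "Decrease in white blood cell counts of grades 3 and 4 may result in transient or permanent treatment discontinuation". There are 7 scheduled post-baseline visits in the SAOL phase (V2 to V8) and 5 in the RW phase (V9 to V13), so one patient can show both directions within a phase. With 5 patients planned per RW arm, one misplaced patient is 1/5 = 20% of an arm in that table.

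**Working it through.** The plan states no figure on this point, so there is none to reproduce. The check applies the SAP rule to example values.

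**Inputs from the documents.** The worst-value rule (SAP 7.5.4). Protocol Table 6, patients older than 7 days: white cells 1,000 to 1,499 per mm³ are Grade 3 and below 1,000 Grade 4. Protocol Table 7, same age group: neutrophils below 400 per mm³ are Grade 4.

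**Assumed inputs.** Reference ranges, because the documents give none. All counts are in 10⁹/L. I also read the rule as applied within each phase, because the tables are built by phase.

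**Formula.** The distance of a value v outside the range is d = max(LLN - v, v - ULN, 0), and the value with the largest d is tabulated. A low value x has d = LLN - x. A high value h has d = h - ULN. The high value displaces the low one when h - ULN > LLN - x, that is, when h > ULN + (LLN - x).

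| Parameter, assumed range | Low value x | LLN - x | Displaced by any value above |
|---|---|---|---|
| WBC 4.0-11.0 | 1.2 (Grade 3) | 2.8 | 11.0 + 2.8 = 13.8 |
| WBC 4.5-13.5 | 1.2 (Grade 3) | 3.3 | 13.5 + 3.3 = 16.8 |
| WBC 4.0-11.0 | 0.9 (Grade 4) | 3.1 | 11.0 + 3.1 = 14.1 |
| Neutrophils 1.5-8.0 | 0.3 (Grade 4) | 1.2 | 8.0 + 1.2 = 9.2 |
| Platelets 150-450 | 40 | 110 | 450 + 110 = 560 |

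**Limiting case.** Since x cannot be below 0, any value above ULN + LLN displaces every possible low value:
- White cells: 15 (range 4-11), 18.0 (4.5-13.5), 20.5 (5-15.5) and 23.5 (6-17.5), or 1.32 to 1.36 times ULN.
- Platelets: 550 (150-400), 600 (150-450) and 750 (200-550), or 1.33 to 1.38 times ULN.
- Hemoglobin is less exposed: with an assumed 11-14 g/dL the bound is 25 g/dL, or 1.79 times ULN.

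**Worked patients.**
- WBC 0.9, 7 and 16 (range 4-11): distances 3.1, 0 and 5.0, so the patient is tabulated as high.
- WBC 0.9, 7 and 13 (same range): distances 3.1, 0 and 2.0, so the patient is tabulated as low, and the high value is the one dropped.
- Platelets 20, 300 and 600 (range 150-450): distances 130, 0 and 150, so high.
- Platelets 20, 300 and 500 (same range): distances 130, 0 and 50, so low.

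**After the change.** With the lowest and the highest value tabulated separately, each of these four patients counts once as a shift to low and once as a shift to high.

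**The case against.** The strongest reply is that the low value remains visible elsewhere.

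- The CTCAE shift tables use the worst grade and separate the directions, so a severe low count appears there if the parameter is graded.
- The by-visit statistics show the minimum at each visit.
- Every out-of-range value is listed by patient, and with at most 15 patients enrolled and about 10 randomized the listing can be read in full.
- Under Protocol 17.6, clinically significant abnormalities that meet the adverse event definition are recorded as adverse events. SAP 7.5.2 tabulates these by severity, and SAP 7.5.3 lists those leading to withdrawal, interruption or dose reduction.

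Most of this stands, and it sets the size of the point. Two gaps remain. The CTCAE tables cover only unnamed parameters, so cover for white cells, neutrophils and platelets is likely but not guaranteed, and an ungraded parameter has no other categorical shift table. The by-visit statistics take an unscheduled value only when it falls in a visit window with no nominal-visit data (SAP 7.1.3).

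A reader might infer that severe leukopenia or thrombocytopenia will generally be reported as high, or will vanish from the laboratory safety report. The documents do not support that. Displacement needs a low value and a sufficiently high value of the same parameter in the same patient and phase, and the displays above keep the low value in the report.

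A reader might also infer that the worst-value rule defeats the secondary endpoint "Improvement in serum albumin and liver transaminases, anemia and/or platelet count (if present at baseline"). That does not follow either. A worst-value shift is a safety display and is not meant to show recovery; the SAP does not present it as the analysis of that endpoint. By-visit changes from baseline (SAP 7.5.4) and improvement in the mAIDAI transaminitis and cytopenia items (SAP 7.4.4.4) cover part of it.

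**Conclusion.** The point holds for the 3x3 tables only. Their rule drops one of two abnormalities whenever a patient has both directions of a parameter in a phase. For white cells and platelets, under the ranges tried, a high value of about 1.3 to 1.4 times ULN is enough to displace even the most extreme low count. The thresholds rest on assumed ranges and will move with the laboratory's own age-specific limits; the formula does not depend on them. How often it would happen cannot be estimated from the documents.

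This is a minor safety-reporting correction. It touches neither the primary analysis nor the fixed-sequence tests, and no data are lost. The absence of a summary restricted to patients with abnormal albumin, transaminases, hemoglobin or platelets at baseline is a separate, small specification point and adds nothing to this one.

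**What to change.** In SAP 7.5.4, replace the single worst value by two. For each parameter and phase, present one 3x3 table from baseline category to the category of the lowest post-baseline value in that phase, and one to the category of the highest. State that white cells, neutrophils, platelets and hemoglobin are among the CTCAE-graded parameters, and preferably list all graded parameters.

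The cost is a short change of SAP wording and one extra table per parameter in each phase. No new data are needed, and the change can be made before database lock and unblinding. A patient with both abnormalities will then appear in both tables, so a footnote should say that the two tables are not to be added together.

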14.3 Baseline visit at Week 0 (V1- Treatment Initiation) – SAOL Phase

- Reassessment of inclusion and exclusion criteria prior to treatment with Tadekinig alfa start
 - Physical examination with specific assessment of hepatosplenomegaly and vital signs
 - Treatment start with Tadekinig alfa
 - Review of AEs and concomitant medications
 - Clinical evaluation by the physician using the mAIDAI
 - Physician Global Assessment (PGA)
 - Patient` s/caregiver`s qualitative evaluation of health status (study specific questionnaire for all patients implemented in protocol version 6)
 - Local Tolerability Index Assessment by Investigator
 - Ophthalmic examination will be performed for the diagnosis (presence/absence), severity and evolution of uveitis and occurrence of ophthalmic adverse events (i.e. toxic neuropathy)
- Lab testing (Samples taken prior to treatment)
 - Hematology, clinical chemistry, ESR (at local lab), urinalysis, CRP, Ferritin,
 - Coagulation (Thrombocytes, Fibrinogen, D-dimer, PTT, PT)
 - Urine pregnancy test, as applicable
- Specialized lab testing
 - Serum: Total IL-18, free IL-18, IL-18BP (Samples taken prior to treatment)
 - Serum: Anti-Tadekinig alfa antibodies (measurement performed on blood drawn before Tadekinig alfa administered for all patients)
 - Additional sample for PK study will be collected at 2 h, 4 h, 6 h and 24h post treatment. Trough levels are calculated based on blood samples used for lab testing (no extra sample needed)
- Treatment initiation

- Two-hour patient observation after first treatment

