At V0 and V1, patients will undergo a physical examination, measurement of vital signs, and routine laboratory testing (including hematology, clinical chemistry, urinalysis, erythrocyte sedimentation rate [ESR], CRP, and coagulation panel). Biological evaluation and genetic diagnosis of auto-inflammatory conditions (NLRC4-MAS, XIAP deficiency, and other monogenic associations with MAS) will be done at V0 (screening visit). Samples for flow cytometry for suspected XIAP deficiency will be analyzed during the screening period and prior to V1. Complete medical and disease history will also be collected during V0. In addition, prior to initiation of therapy, cytomegalovirus (CMV)

and Epstein-Barr virus (EBV) tests, serology tests, and a complete infectious workup will be performed.

Specific laboratory determinations such as total and free IL-18 and IL-18BP will be performed at V1 and subsequent visits.

The global disease activity will be assessed by the mAIDAI. The mAIDAI will be applied at all study visits and will be available for review throughout the study. For the evaluation of response to therapy and disease reactivation, only the objective parameters of the mAIDAI will be taken into consideration. A Physician Global Assessment (PGA) tool will also be applied at all study visits by the physician to assess the global disease status. The patient's or caregiver's evaluation of the health status questionnaire will be applied at V1 and the end of the SAOL phase.

Assessments during the SAOL phase (V1 to V8) will include complete physical examination, review of all adverse events (AEs), and routine and specific laboratory analysis. Samples for anti-drug antibodies (ADAs) will be collected at Baseline of SAOL (V1), Week 2 (V3), Week 4 (V5), Week 12 (V7), and Week 18 (V8).

6.1.3 Randomized Withdrawal Phase:

All patients who have completed 18 weeks of treatment during the SAOL phase and showing a partial or complete response at Week 18 (V8) will be randomized in a 1:1 ratio to begin treatment in the RW phase. Patients will receive the study treatment (placebo or TA) for up to an additional 16 weeks. Experiencing a disease reactivation at any point during the 18-week SAOL phase will not prevent a patient from enrollment into the RW phase; rather, patients are required to meet the criteria for ongoing TA treatment throughout the SAOL phase and show a partial or complete response at Week 18 (V8).

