6.4.2 Description of Safety and Tolerability Variables

Safety and tolerability variables include the following:

- Adverse events (including adverse events of special interest [AESI])
- Physical examination findings including an ophthalmological examination (ie, clinically significant changes from Baseline)
- Vital signs (ie, clinically significant changes from SAOL Baseline for data collected during the SAOL phase and RW Baseline for data collected during the RW phase)
- Laboratory assessments including clinically significant changes from SAOL Baseline for data collected during the SAOL phase and RW Baseline for data collected during the RW phase in hematology with platelet counts, CRP, ESR, ferritin, fibrinogen, D-dimer, liver enzymes, creatinine, and glomerular filtration rate

- Immunogenicity evaluation: Generation of anti-rh-IL-18BP antibodies
- Local tolerability at the injection site, as evaluated by a standardized assessment

An AESI for this study is defined as an event that constitutes an injection site reaction, including pruritus, erythema, and swelling.

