7 STATISTICAL METHODS

7.1 General Methodology

Data will be analyzed by Precision for Medicine biostatistics personnel. Statistical analyses will be reported with tables, figures, and listings, presented in rich text format, and using recommended ICH numbering. Output specifications for all tables, figures, and listings will be in conformance with guidelines specified by the ICH in Appendix 7 of the *Electronic Common Technical Document Specification* (Apr 2003).

7.1.1 *Reporting Conventions*

Tables and figures will be summarized for all patients combined during the SAOL phase and by treatment group during the RW phase. Tables summarizing demographics and other baseline characteristics for the RW phase will also include a column for all patients combined. Where applicable, separate summaries will be presented for each study phase (SAOL and RW). In general, all data collected and any derived data will be presented in patient data listings, for all enrolled patients. Listings will be ordered by site, patient number, treatment group, and assessment or event date. The treatment group presented in listings will be based on the planned assignment, unless otherwise noted.

In general, continuous variables will be summarized to indicate the study population sample size (N), number of patients with available data (n), mean, SD, median, 25th (Q1) and 75th (Q3) quartiles, minimum, and maximum values. Selected continuous efficacy variables will also be summarized by the 95% CI of the mean. Categorical variables will be summarized by the population size (N), number of patients with available data (n), number of patients in each category, and the percentage of patients in each category. Unless otherwise noted, the denominator to determine the percentage of patients in each category will be based on the number of patients with available data. Selected ordinal data may be summarized using both descriptive statistics and counts and percentages of patients in each category, as appropriate.

Non-zero percentages will be rounded to one decimal place. Rounding conventions for presentation of summary statistics will be based on the precision of the variable of summarization, as it is collected in its rawest form (ie, on the eCRF or as provided within an external file) and are outlined as follows:

- The mean and median will be rounded to one more decimal place than the precision of the variable of summarization

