- Measures of variability (eg, SD, SE) will be rounded to two more decimal places than the precision of the variable of summarization
- Minimum and maximum values will be presented using the same precision as the variable of summarization

Other statistics (eg, CIs) will be presented using the same general rules outlined above or assessed for the most appropriate presentation based on the underlying data.

Statistical significance testing will be two-sided and performed using $\alpha=0.05$. P-values will be reported for all statistical tests, rounded to four decimal places. P-values less than 0.0001 will be displayed as “<0.0001”; p-values greater than 0.9999 will be displayed as “>0.9999”.

7.1.2 *Definition of Baseline*

Changes from baseline, percentage changes from baseline, and occurrence of disease reactivations will be calculated separately within each study phase (SAOL and RW), relative to the start of dosing during that phase:

- **SAOL Baseline:** Baseline during the SAOL phase will be defined as the last measurement reported prior to the first dose of open-label TA at Week 0 (V1)
- **RW Baseline:** Baseline during the RW phase will be defined as the last measurement reported prior to the first dose of double-blind study drug (TA or placebo) at Week 18 (V8)

7.1.3 *Summarization by Visit*

Data summarized by study visit will be based on the nominal, scheduled visit label as reported on the eCRF, except for data that are captured at early termination or unscheduled visits. Data collected at early termination or unscheduled visits will only be included in by-visit summaries if they fall within a scheduled post-baseline visit window (see Table 2) and there is no data from a nominal visit for that specific visit. If both an unscheduled visit and an early termination visit fall within the same visit window the early termination visit will be used for that specific visit.

Table 2 Visit Windows for Early Termination and Unscheduled Visits

Phase	Analysis Visit	Target Day	Visit Window
SAOL	Week 1	SAOL Day 7	$2 \leq \text{SAOL Day} \leq 11$
	Week 2	SAOL Day 14	$12 \leq \text{SAOL Day} \leq 18$
	Week 3	SAOL Day 21	$19 \leq \text{SAOL Day} \leq 25$
	Week 4	SAOL Day 28	$26 \leq \text{SAOL Day} \leq 42$
	Week 8	SAOL Day 56	$43 \leq \text{SAOL Day} \leq 70$
	Week 12	SAOL Day 84	$71 \leq \text{SAOL Day} \leq 105$
	Week 18	SAOL Day 126	$106 \leq \text{SAOL Day} \leq \text{End of SAOL Phase}$
	Week 20	RW Day 14	$2 \leq \text{RW Day} \leq 21$

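### The SAP tabulates anti-drug antibodies only as continuous levels and changes, and plans no count of patients who develop antibodies after the pre-dose V1 sample

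*SAP*

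**What the plan says.** SAP 6.4.2 lists the endpoint as "Immunogenicity evaluation: Generation of anti-rh-IL-18BP antibodies". Protocol 8.5.1 lists the same endpoint. Neither document says what makes a patient positive or newly positive.

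Under SAP 7.5.5.4, antibody blood levels "will be summarized by treatment group, separately for each study phase". The content of the tables is then given: "Descriptive statistics will be presented for results and change from phase-specific baseline at each visit where blood samples were scheduled for collection". The same section adds a plot of each patient's level over time. SAP 7.1.1 puts all data in patient listings and defines the summary of a continuous variable as N, n, "mean, SD, median, 25th (Q1) and 75th (Q3) quartiles, minimum, and maximum values".

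SAP 7.1.2 sets two baselines. For the open-label (SAOL) phase it is the "last measurement reported prior to the first dose of open-label TA at Week 0 (V1"). For the randomized withdrawal (RW) phase it is the "last measurement reported prior to the first dose of double-blind study drug (TA or placebo) at Week 18 (V8").

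In the open-label phase samples are "collected at Baseline of SAOL (V1), Week 2 (V3), Week 4 (V5), Week 12 (V7), and Week 18 (V8"). In the RW phase they follow at V10, V11 and V13. Protocol 14.3 confirms that the V1 antibody sample is drug-free: "measurement performed on blood drawn before Tadekinig alfa administered for all patients".

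SAP 7.1.4 has a general rule for results reported as below a limit: the sign is dropped and the number is used. There is no separate rule for antibodies.

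**The concern.** Generation of antibodies happens or does not happen in a patient, so its natural summary is how many patients, out of how many exposed, became positive after starting the drug. The stated method gives the distribution of a level instead. A mean or median level does not determine how many patients converted.

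The two-phase layout adds a second gap. Every patient in the RW phase, including those on placebo, has had 18 weeks of Tadekinig alfa. Antibodies formed in that time are already in the V8 baseline, and the placebo column carries antibodies formed on active drug. No planned table follows patients from V1 through both phases.

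At stake is a named safety endpoint of a biologic. With no positivity rule in the SAP, whoever reads the plots has to choose one after seeing the data, whereas SAP section 4 states that the plan exists to prevent choices of that kind. The SAP does count patients for comparable safety data: skin rash and local tolerability get numbers and percentages, and laboratory tests get shift tables.

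**Working it through.** The documents state no figure for this point, so there is none to reproduce. The check is of text, with an illustration on assumed levels.

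**Exposure before V8.** The schedule is one dose every 2 days, and V8 is Day 126: 126 / 2 = 63 scheduled doses. The Schedule of Events places the last open-label dose 2 days before V8.

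**Which planned display answers which question**

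| Display | Reference | Shows | States how many developed antibodies? |
|---|---|---|---|
| SAOL change | V1, pre-dose | rise in level over 18 weeks | no |
| RW observed values | none | level at each visit, by arm | no |
| RW change | V8 | change after randomisation | no, and excludes antibodies formed before V8 |
| Individual plots, listings | none | every value for every patient | only if the reader supplies a cut-point |

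**Illustration.** Assumed: 10 patients, all at level 1 (negative) at V1; positive patients at level 10 unless stated.

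- *A. Three patients convert before V8 and stay positive.* Mean change V1 to V8 = 3 × (10 − 1) / 10 = 2.7. Each patient's change from V8 is 0, so the mean RW change is 0.0 in either arm, however they are allocated. The SAOL change and the RW observed values show the antibodies; the RW change does not.
- *B. One patient reaches level 28 instead.* Mean change V1 to V8 = (28 − 1) / 10 = 2.7, as in A. The median level at V8 is 1 in both. The maximum differs (28 against 10) and so does the upper quartile (1 against 7.75, by linear interpolation), but neither states that one case has one converter and the other has three.
- *C. From A, two of the three positives revert during RW and two negatives convert.* Mean change from V8 over the ten = (2 × 9 − 2 × 9) / 10 = 0.0, despite two new positives. Within an arm the cancellation occurs only if gains and losses fall together. If both conversions were in one arm of five and both reversions in the other, the arms would show +18/5 = +3.6 and −18/5 = −3.6. Counted since V1, 3 + 2 = 5 of 10 patients developed antibodies.

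**What a count would report.** Exact (Clopper-Pearson) 95% intervals for assumed counts; the trial enrols at most 15 and expects at least 10 randomised:

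| Newly positive / N | % | 95% CI |
|---|---|---|
| 0/10 | 0 | 0 to 30.8 |
| 3/10 | 30 | 6.7 to 65.2 |
| 5/10 | 50 | 18.7 to 81.3 |
| 2/12 | 17 | 2.1 to 48.4 |
| 0/15 | 0 | 0 to 21.8 |
| 3/15 | 20 | 4.3 to 48.1 |

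Even zero positives among 15 would leave rates up to 21.8% open. A table of levels does not convey that.

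**The case against.** The strongest reply is that the information is already there. With at most 15 patients, individual plots over time and full listings let a reader see each patient's course. The SAOL table is measured from the drug-free V1 sample over the first 18 weeks. The RW tables give observed values as well as changes. Phase-specific baselines are the SAP's general rule, and in a withdrawal design change from V8 is the right reference for what happens after randomisation. SAP section 4 also mentions table templates, which are not in the supplied text and could contain a count.

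Much of this stands, and it rules out several stronger readings that a reader might infer:

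- That the tables cannot show antibody formation at all. They can: the SAOL change from V1 tabulates a rise in level.
- That a patient who is positive and stable contributes nothing to the RW tables. That patient contributes zero to the change rows only; the level appears in the observed rows.
- That only means are planned. Median, quartiles, minimum and maximum are planned too, and one or two high values would appear in the maximum.
- That V8 is a wrong baseline. It is legitimate for its own question, and replacing it outright would put 18 shared weeks of exposure into both arms and lose the post-randomisation contrast.
- That most patients will be negative. The documents give no antibody rate.

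What the reply does not supply is a rule for who counts as positive, or the resulting number. Plots and listings leave both to be decided after the results are seen. The general rule for below-limit results enters them in the level tables as ordinary numbers and does not classify them.

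**Conclusion.** The concern holds in a limited form. For a named safety endpoint that is an occurrence, the SAP text states a method that summarises levels and does not estimate how many patients developed antibodies. Separately, the RW change from V8 cannot reflect antibodies formed during the 18 open-label weeks that both arms share. The data are collected and displayed; the missing parts are the definition and the count.

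The size cannot be taken from the documents. On assumed counts the unreported result would be, for example, 17% (2.1% to 48.4%) for 2 of 12, or 0% (0 to 21.8%) for 0 of 15. The levels 1, 10 and 28 in the illustration are also assumptions. The conclusion that no count is planned applies to the SAP text and not to table templates that were not supplied. No efficacy result, error rate or sample size is affected, so this is a reporting change that should be made before unblinding.

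**What to change.** In SAP 7.5.5.4:

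- Define antibody-positive by the assay's positivity cut-point, and newly positive relative to the V1 pre-dose sample. Fix both before unblinding.
- State how results below the assay limit are handled.
- Add one table of n/N (%) antibody-positive and newly positive since V1, by visit and cumulatively across both phases, with exact 95% CI. In the RW phase give it by arm, with each patient's V8 status listed.
- Keep change from V8 as a secondary display of antibody change after randomisation.

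The cost is one paragraph, one table and obtaining the cut-point, which the supplied documents do not give. No sample, visit, test or alpha changes. The counts will be small and the intervals wide, above all by arm with about five patients each, so the table is descriptive. That is also why V8 status is better listed by patient than used to split the arms further.
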